delivered by the research team. The first session will focus on the physical literacy of older adults and the second session will focus on how to lead functional fitness training under the FITT principle (Frequency, Intensity, Time, Type; and how they relate to cardio, strength, stretching and injury prevention) for older adults. A further important issue that will be mentioned is related to ensuring the safety of older adults during the whole intervention, which will emphasize the process-oriented outcomes and encouragement to participation, rather than the product oriented assessments. Meanwhile, the main goal of functional training is to improve the range of joint motion, increase muscle strength and flexibility, and boost blood circulation in a safe and acceptable manner. Therefore, symmetry training together with cardiovascular training is the core of the training program. Examples of the main training activities include cardio-fullbody exercises (e.g. move adherence to the music training, including running, jogging, dancing movements, etc.), upper body exercises (e.g. bench press, rowing and lifting), lower body exercises (e.g. squatting and lateral hurdle jumps with tap-sensitive pods) and sensory integrative training (e.g. shooting training with an electronic sensory wall).

Part 2: Mastering physical literacy class (MPLC)

A 30-minute MPLC program will be conducted by experienced elderly health and fitness instructors after WBFFT. This MPLC program aims to enhance the knowledge and understanding of physical literacy. Referring to the newly developed consensus statement (10), the MPLC includes the following five domains related to the relationship with movement and physical activity throughout life:

- i. Why physical literacy matters – improves health, well-being and quality of life.
- ii. Understanding physical literacy – value, enjoy and engage in physical activity for life.
- iii. Everyone's physical literacy is different – their individual needs and experiences of movement and physical activity.
- iv. Building physical literacy – think, feel, move and connect with others.
- v. How experience affects physical literacy – people, places and spaces around us.

Part 3: Daily-based reflective writing (DBRW)

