Daily-based reflective writing or keeping a journal has been widely used in interventions targeted at older adults, especially within the affective domain. Life review through writing, which includes written or verbal prompts to encourage writing about one's life in a systematic, chronological way irrespective of emotional content is a valuable intervention that can be used in occupational therapy practices with the elderly. Previous randomized controlled trials have shown support for the therapeutic benefits of emotional disclosure through writing in not only adults with chronic illness but also in healthy adults (11).

At the end of the baseline stage of this proposed study, each participant of the intervention group will receive a template notebook for daily-based reflective writing. The required columns consist of the daily diet, physical activity, mood and sleep quality. Participants will be required to write down their behavior in this notebook daily. In each week's functional training course, there will be a life-sharing session, where the

participants will be reminded to bring their notebooks and share their daily activities with others. They will receive feedback, advice and encouragement from the instructor and each other. The notebook will be collected during the last week of the intervention.

Part 4: Buddy peers support group (BPSG)

Providing strong social support for older people in Hong Kong may lead to a high level of relatedness that may increase well-being and better physical health (12). The BPSG introduced in this program may greatly increase social support which will be shown to be a key determinant of adherence to the exercise programs and create a commitment to achieve specified levels of physical activity (13).

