In this proposed study, peer-support groups with buddy members will be arranged in each daycare center. Three pairs of buddies and hence about 6 participants will be formed per group. A total of 6 buddy pairs and 2 groups will be formed per daycare center. Buddy peers will encourage each other to do functional exercises regularly or to perform functional exercises together. The time and place for the practice will be decided among buddy members. A member in each group will be nominated as the leader to assist in the liaison and coordination of group activities. The group will perform weekly group-based functional exercises, and the time and place for the practice will be decided among group members. The group will be encouraged to hold monthly gatherings with their fitness instructor in order to strengthen social support.

Study design

A two-arm cluster randomized controlled trial will be employed in this proposed study (see details in Fig 1). According to the Social Welfare Department of Hong Kong, there are 98 daycare centers for the elderly in 2023 (14). Daycare centers for the elderly located in 3 regions in Hong Kong will be invited to participate in the intervention. The PLBI will be conducted for twelve weeks.

Sample size and participants

The required sample size is calculated based on the hypothesized effect sizes, and the likely rates of participant drop-out for the outcomes. The estimated sample size is 198 with an effect size of 0.25, α of 0.05 and power of 0.95 (15). With the anticipation of a 20% participant drop-out rate, this led to a required number of 120 participants per group. Therefore, 10 daycare centers for the elderly in Hong Kong will be invited to participate in this study.

Physical literacy-based intervention group (PLBI)

Inclusion criteria will be: 1) those aged 65 to 74 years old who are registered in a daycare center/unit for the elderly in Hong Kong, 2) the ability to walk eight meters without assistance (16), and 3) able to read and write. Exclusion criteria will include 1) neurological disease which impairs mobility, cardiovascular disease which results in shortness of breath or angina on walking up one flight of stairs, and 2) cognitive impairment. Participants' cognitive function will be screened by the Chinese Mini-Mental State Examination (17, 18), and those who score below 24 will be excluded.

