SPSS version 28 for Windows will be used for data analysis. Internal consistency reliability coefficients (Cronbach alpha) will be calculated for all sub-scales within the psychometric questionnaires. A cut-off score of 0.7 will be used to determine acceptable reliability. Descriptive statistics (means and standard deviations) will be calculated for participants' primary and secondary outcomes (objective and self-reported) at three-time points. Multilevel modeling methods were used to account for the clustered nature of the data. Specifically, we used three-level (time within older adults within daycare center) regression analyses to examine the effects of group (experimental vs control), time (baseline, post-test and follow-up), and the group-time interaction (i.e., "intervention effect") on the primary and secondary outcomes. Covariates such as age, gender, BMI, education, and socioeconomic status will be included in the analysis. Bonferroni post hoc analyses will be conducted to determine contributing factors to the significance of F values, and the confidence level will be set at 95% to maintain statistical reliability for all the analyses.

Evaluation plan

At post-intervention, in-depth interviews of a group of 8 - 12 participants will be conducted to explore their experiences in participating in the intervention, the level of satisfaction with the intervention, and the barriers and expediter in performing the PLBI as instructed. DBRW will also be material for evaluation analysis. The reasons why participants dropped out of the study will also be recorded. Additionally, participants will be invited to fill in a process evaluation survey which assesses their level of involvement and level of satisfaction with the intervention.

Reference

1. Morgan K. Applying the TARGET Pedagogical Principles in Physical Education to Enhance Students' Physical Literacy. *Journal of Physical Education, Recreation & Dance*. 2019;90(1):9-14.

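### No falls, injuries or other medical events are scheduled to be recorded in either arm, so there is no comparable event count for participants who stay in the trial

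*Combined protocol and SAP*

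**What the plan says.** **Exposure.** Part 1 (WBFFT) describes instructor-led sessions twice a week for 12 weeks in the daycare centres. Its examples include "lower body exercises (e.g. squatting and lateral hurdle jumps with tap-sensitive pods". Part 4 (BPSG) adds buddy and group practice at times and places that the members choose. Under Control group, controls receive the same programme once data collection is complete.

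**Safety.** Part 1 makes safety a topic of the instructor workshop: "A further important issue that will be mentioned is related to ensuring the safety of older adults during the whole intervention". The eligibility criteria exclude certain neurological and cardiovascular disease and cognitive impairment. These are preventive steps.

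**Measurement.** Outcome measures sets visits at weeks 0, 12 and 18. Data analysis covers the primary and secondary outcomes.

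**Items that might touch on harms.**
- Evaluation plan: "The reasons why participants dropped out of the study will also be recorded". No arm is specified. The same section has interviews with 8 to 12 participants, and a process survey described as covering involvement and satisfaction.
- Part 3 (DBRW), intervention arm only: a weekly meeting at which "there will be a life-sharing session", and a daily notebook. On the notebook: "The required columns consist of the daily diet, physical activity, mood and sleep quality" and "The notebook will be collected during the last week of the intervention".
- Part 4, intervention arm only: "A member in each group will be nominated as the leader to assist in the liaison and coordination of group activities" and "The group will be encouraged to hold monthly gatherings with their fitness instructor in order to strengthen social support".

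**The concern.** Readers deciding whether to adopt an exercise programme for older adults will want its harms beside its benefits. Harms data that were not collected cannot be supplied at the analysis stage, which makes this more than a missing detail in the write-up.

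The asymmetry between arms matters as much as the gap itself. Intervention participants meet an instructor twice a week, share their activities in a group and keep a notebook. Controls have no equivalent contact through the trial. Any events that surfaced informally would come mainly from the exercising arm and could make it look worse than it is. A lack of reports could not be read as safety either. Controls then take up the same programme without a harms comparison having been made.

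**Working it through.** The plan states no harms figure, so there is none to reproduce. The check is a read-through of every place where an event could be recorded, plus simple arithmetic on coverage.

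**Step 1. Outcome instruments.** Outcome measures names seven: SPPB, accelerometer, IPAQ short form, MoCA-B, PPLI, PWB and the Friend Support subscale. Number described as asking about falls, injuries or medical events: 0 of 7. The SPPB and the physical well-being items of the PWB are taken in both arms and could reflect a lasting decline, but they do not identify or count events.

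**Step 2. Visits.** There are two post-baseline visits, weeks 12 and 18. Number with a scheduled event question: 0 of 2, in either arm.

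**Step 3. Other channels, side by side.**

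| Channel | Intervention arm | Control arm | Described as recording events? |
|---|---|---|---|
| Drop-out reasons | yes | yes (no arm limit stated) | only if the event is why the person left |
| Supervised sessions, twice weekly | yes | no | no |
| Weekly life-sharing | yes | no | no |
| Notebook | yes | no | no; diet, activity, mood, sleep |
| Group leader, monthly gatherings | yes | no | no |
| Interviews | 8 to 12 people, about experience of the programme | none described | no; experience, satisfaction, barriers |
| Process survey | arm not specified | arm not specified | no; involvement, satisfaction |

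**Step 4. What drop-out reasons can reach.** Inputs from Sample size and participants: 120 per arm, 20% drop-out, taken here as equal in both arms.
- Expected leavers per arm: 120 × 0.20 = 24.
- Expected stayers per arm: 120 − 24 = 96.

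Drop-out reasons therefore give no information on about 96 of 120 participants in each arm.

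**Step 5. Reach of the intervention-arm channels, even if they were used.**
- Notebook: kept for the 12 intervention weeks, so at most 12/18 = 67% of the trial period in that arm and 0/18 in control.
- Interviews: 8/120 = 6.7% to 12/120 = 10% of the arm.

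**Step 6. Coverage with identical questions in both arms.** The week-12 visit looks back 12 weeks and the week-18 visit looks back 6: 12 + 6 = 18 weeks for a participant who attends both. Someone who leaves at week 5 and gives a reason contributes 5 weeks. Someone who cannot be reached after baseline contributes none.

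**The case against.** **The drop-out reasons are a both-arm harms record.** This stands in part. A reader might infer that the trial can report nothing on harms by arm. The documents do not support that: the sentence on drop-out reasons is not limited to one arm, so injury-related withdrawals could be tabulated by arm. What is missing is a comparable count among those who stay.

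**Safety is not neglected.** Also true. Sessions are guided by qualified instructors in the centres, the workshop covers injury prevention, people at evident risk are excluded, and the hurdle jumps are only one example among several activities. A reader might infer that the programme is unsafe or that the team ignored risk; nothing in the documents shows either. But prevention lowers risk without recording what happens.

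**A reporting route may exist elsewhere.** Some pages are not in the public text, so one cannot infer that no incident reporting exists. Spontaneous reporting would still not put the same questions to both arms over the same period.

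**The process survey might include such items.** Its items are not shown. Its stated purpose makes event questions unlikely, and the plan does not assign them to it.

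**Size.** With no event rate in the documents, the figures above describe coverage and not missed events. That limit is accepted.

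**Conclusion.** The point holds in this form: the plan schedules no recording of falls, injuries or other medical events in either arm, and so gives no comparable event count for participants who remain. On the plan's own figures that is about 96 of 120 per arm, assuming that 20% drop-out applies equally to both arms. Injury-related withdrawals could still be counted by arm from the drop-out reasons.

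The efficacy analysis is not affected. A reader might go further and infer biased efficacy results or a particular number of undetected injuries; the documents support neither.

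The conclusion rests on the protocol and SAP body as published and on the instruments as described there. It is an improvement that should be made, and it does not invalidate the trial.

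**What to change.** **Change.** Add a short set of falls, injury and medical-event questions, with fixed wording that does not refer to the classes, asked identically in both arms:
- at the week-12 visit, covering the period since baseline;
- at the week-18 visit, covering the period since week 12;
- when a drop-out reason is recorded, covering the period since the last visit.

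Report event counts and drop-out reasons by arm descriptively. Any interval should allow for clustering by centre; with 10 centres it should be read cautiously. State how many participants gave the full 18 weeks and where coverage stopped for those who left.

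A weekly instructor log in the intervention arm is not part of this fix. It would do nothing for the comparison, and the extra prompting could raise reporting in that arm. If the sponsor wants one for safety oversight, it should be justified on that ground and kept out of the arm comparison.

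**Cost.** A few questions at visits that already take place, and one descriptive table. The downsides to state with the results are slightly longer visits, recall over up to 12 weeks, and self-report by participants who know their arm. Blinding is stated for the assessors of the objective measures; it is not clearly stated for the research assistants who administer the self-report measures.

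**If fieldwork is already complete.** The text mixes future and past tense, so this is possible. The questions could not then be added. The sponsor could still tabulate drop-out reasons by arm, say plainly that harms were not systematically collected, and record events when controls receive the programme.
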